#### 3.1.2 Outcome measures

Primary outcome measure: Number of missed cases of CDI - Comparison of test result at participating site and test result at European Coordinating Laboratory (using optimised testing). Objective 1.1

Secondary outcome measures:

- Number of missed cases of CDI Comparison of test result at participating site and test result at European coordinating laboratory (using novel highly sensitive C. difficile assay for toxins A and B).
- Types of *C. difficile,* as measured by PCR-riboyping, toxinotyping and whole genome sequencing. Objective 1.2

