#### 3.1.6 Data collection

In addition to the laboratory data, data will be collected on the following variables;

- Sample source sites (hospital/GP, nursing home)
- CDI test result for that sample at the submitting laboratory

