#### 3.1.7 Data analysis

Results of the CDI testing at the ECL will be compared with the original result at the participating site, with 'missed' diagnoses recorded (either due to false negative result at participating site, or sample not tested at participating site). Results of 'missed' diagnoses will be compared between countries and sample source sites (hospital/GP/nursing home). In addition, the number of co-infections and alternative GI pathogens (in CDI negative samples) will be compared between countries and sample source sites, to determine difference between in-patient and community populations.

Types of *C. difficile* (by PCR-ribotyping, and toxinotyping) will be compared between countries, settings (community/hospital), cases/colonised participants and those detected by different commercial testing methodologies (optimised method vs SiMoA). Whole genome sequencing will be used to examine the true relatedness of strain types within and between settings (community/hospital). Comparison will be made between the types of *C. difficile* isolated from human, environmental and food sources. In addition, whole genome sequencing will be used to examine the true relatedness of strain types between sources.

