# *Highlight current guidelines for disease detection, notification and management/control Objective 2.1*

Five international societies have recently issued/updated guidelines on diagnosis, prevention, treatment and control of CDI.20,34-37 This reflects the increasing burden of CDI worldwide, new knowledge, and because some issues remain contentious. Underdiagnosis, as reported by our EUCLID study is a main contentious area. Underdiagnosis can depend on suboptimal laboratory testing for CDI and/or lack of suspicion by some clinicians, which could be overcome by automatic testing for CDI on every liquid stool sample. Overdiagnosis of CDI is also a challenge; it is important to distinguish CDI infection from colonization in hospitalised patients with diarrhoea.

One of the pillars of control of CDI is communication through reporting, but notification represents another conundrum not addressed by guidelines. In many countries, both in community and healthcare settings, there is mandatory notification for infectious diarrhoea, but not for CDI. In a recent systematic survey of clinical practice guidelines, showing that recommendations are often not consistent with available evidence, there is no mention of notification strategies for CDI.

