#### 3.5.7 Data analysis

Comparisons of knowledge and compliance with guidelines for disease detection, notification and management/control will be made between countries and healthcare settings (community/hospital). Particular attention will be focussed on the dates of policies and the length of time it takes for European/national guidance to filter down to a local level. This may highlight a possible area for improvement in guideline communications.

Comparisons between testing policies and methodologies will be made between countries and healthcare settings (community/hospital). In addition, data from 1.1 on 'missed' case rates in these settings will allow identification of 'poor practice'.

Data will be compiled on current surveillance programmes for CDI and compliance with these, in different countries and settings. This will be used to determine a 'best-practice model' for surveillance and investigate mechanisms for increasing engagement with surveillance.

Comparisons of knowledge and compliance with guidelines for treatment pathways will be made between countries and healthcare settings (community/hospital). In particular comparisons will be made of risk stratification of patients (via severity criteria) between different healthcare settings and countries. Again this will be used to determine a 'best-practice model' for risk stratification.

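### Only missed diagnoses are counted, so the 'poor practice' label in Protocol 3.5.7 cannot detect over-diagnosis, although the data to count it are collected

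*Protocol*

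**What the plan says.** The primary outcome of the sample collection study (Protocol 3.1.2) is "Number of missed cases of CDI - Comparison of test result at participating site and test result at European Coordinating Laboratory (using optimised testing"). The first secondary outcome repeats it with the novel toxin assay. Protocol 3.1.7 defines a missed diagnosis by two routes, "either due to false negative result at participating site, or sample not tested at participating site", and continues: "Results of 'missed' diagnoses will be compared between countries and sample source sites (hospital/GP/nursing home").

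Protocol 3.5.7 plans a comparison of testing policies and methods between countries and settings. It adds that "data from 1.1 on 'missed' case rates in these settings will allow identification of 'poor practice".

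The rationale for Objective 2.1 (Protocol 3.5.1) accepts that error runs both ways. After discussing underdiagnosis it calls overdiagnosis a challenge too, and says "it is important to distinguish CDI infection from colonization in hospitalised patients with diarrhoea".

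The data for both directions exist. Protocol 3.1.6 collects the "CDI test result for that sample at the submitting laboratory", and Protocol 3.1.3 and 3.1.4 send every unformed stool received on the sampling day to the central laboratory, whatever test was requested.

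**The concern.** A comparison of two test results has two kinds of disagreement. The plan names, counts and uses only one. No outcome or analysis in the protocol or SAP covers a stool reported as CDI by the site and found negative centrally. The mortality comparison in Protocol 3.2.2 has the same shape: it sets correctly diagnosed patients against missed ones and has no over-diagnosed group.

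This matters because the missed rate is given an evaluative use in 3.5.7. Among the stools a site tests, the missed rate can be lowered by calling CDI more freely, for example by reporting every stool that carries the organism. A country or setting that does so cannot be flagged, whereas one that uses the recommended algorithm with imperfect sensitivity can. Objective 2.2 concerns variation in testing and in following guidance, and a measure blind to one error type gives a lopsided answer. The study also could not state net local misreporting, meaning missed minus over-called.

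**Working it through.** **1. Which cells are counted**

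| Local result | Central positive | Central negative |
|---|---|---|
| Positive | agreement | no category in the plan |
| Negative | missed (3.1.7) | agreement |
| Not tested | missed (3.1.7) | no diagnosis made |

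The missed rate uses only the central-positive column. It does not change with the number in the local-positive, central-negative cell.

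**2. The plan's own figures (Protocol 3.1.5)**

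The inputs are 1620 samples per sampling day, 10% toxin positive (stated as 240) and about 15% culture positive (stated as 252).

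- 1620 × 0.10 = 162, not 240. The stated 240 would need 240/1620 = 14.8%.
- 1620 × 0.15 = 243, not 252. The stated 252 would need 252/1620 = 15.6%.

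Neither count follows from its rate. That is a separate matter, but it means the size has to be given on both readings.

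**3. Stools open to over-calling, per sampling day**

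These are culture positive but toxin negative. The subtraction assumes that every toxin-positive stool is also culture positive.

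- From the rates: 243 − 162 = 81.
- From the counts: 252 − 240 = 12.

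Non-toxigenic strains must be taken off both figures. The documents do not give their share.

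**4. Three local policies compared**

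The call rates are assumptions for illustration. Every stool is taken to be tested locally. A: sensitivity 85%, no over-calls. B: every culture-positive stool called CDI. C: all toxin positives and half of the remaining culture positives called CDI.

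| Reading | Policy | Missed | Missed rate | Over-calls | Local positives | Over-calls / local positives |
|---|---|---|---|---|---|---|
| Rates | A | 162 × 0.15 = 24.3 | 15% | 0 | 137.7 | 0% |
| Rates | B | 0 | 0% | 81 | 243 | 33.3% |
| Rates | C | 0 | 0% | 40.5 | 202.5 | 20% |
| Counts | A | 240 × 0.15 = 36 | 15% | 0 | 204 | 0% |
| Counts | B | 0 | 0% | 12 | 252 | 4.8% |
| Counts | C | 0 | 0% | 6 | 246 | 2.4% |

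On either reading the planned measure favours B and C over A, and it cannot separate B from C.

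**5. Effect on burden**

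Central positives are 162 (or 240) under every policy. Local positives minus over-calls plus missed returns the same number: 137.7 − 0 + 24.3 = 162 for A, and 243 − 81 + 0 = 162 for B.

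**6. Precision**

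With 120 sites, 1620/120 = 13.5 samples per site per day, of which 13.5 × 0.10 = 1.35 are toxin positive. Rates for single sites would be unstable in either direction.

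**The case against.** Several points on the other side have force.

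- **Scope.** Objective 1.1 is expressly about missed cases. That explains the primary outcome. It does not justify resting the practice judgement in 3.5.7 on that outcome without its counterpart.
- **Testing policy is compared too.** The preceding sentence of 3.5.7 compares policies and methods, so a site using gene detection or culture alone would be visible. This stands, and the missed rate is not the only information on practice. Knowing the method still does not say how many over-calls it produces.
- **Zero missed is not automatic.** Untested stools count as missed, so liberal calling reaches zero only where every stool is also tested locally. This stands and is a condition of the table above.
- **Central negative is not always a local error.** Protocol 1.4.2 (Objective 1.1) warns that toxin may degrade and give false negatives, and the samples are shipped. In addition, Protocol 3.1.1 calls toxin-negative carriers colonised, while SAP 4.1.1 and 6.1 count toxin-negative patients with a toxigenic strain as a case class (39 of 213 cases in SAP Table 1). An over-diagnosis rate with no stated reference could mislabel sites. This stands and shapes the remedy.

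A reader might go further than the documents allow in three ways. First, that over-calling sites would score as best practice: in 3.5.7 the best-practice models concern surveillance ("This will be used to determine a 'best-practice model' for surveillance") and risk stratification, no ranking is planned, and the units are countries and settings. Second, that burden is inflated: no formula adding missed cases to local counts appears, and central positivity on all stools is untouched by local over-calls. Third, that false cases enter the cost work: patient-level cases are defined centrally, and the documents do not say that site cost data rest on unverified local positives.

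**Conclusion.** The point holds in this form: the plan records one direction of disagreement, uses it to identify poor practice, and never measures the overdiagnosis that its own rationale names. A country or setting that over-calls cannot be flagged on the missed rate.

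The uncounted over-calls range up to 12 to 81 per sampling day (4.8% to 33.3% of local positives). This assumes that every site tests every stool and calls every culture-positive, toxin-negative stool CDI, and that all toxin positives are culture positive. Non-toxigenic strains and less liberal calling would reduce the figures. The width of the range comes from the mismatch between rates and counts in Protocol 3.1.5. The structural conclusion does not depend on where in the range the truth lies.

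The documents do not support extending this to best-practice scoring, to the burden estimate or to costs. It is worth correcting because it bears directly on Objective 2.2 and needs no further data collection.

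**What to change.** 1. **Protocol 3.1.7:** report the full table of local result (positive, negative, not tested) by central result.
2. **Protocol 3.1.2 and 3.1.7:** add a secondary outcome, the proportion of local positives that are centrally negative, with confidence intervals, by country, sample source and local test method.
3. **Central reference:** report this outcome under each definition, namely toxin negative (with the assay named) and negative by all assays including toxigenic culture or toxin gene. State that toxin loss in transit may explain some local-positive, toxin-negative results.
4. **Protocol 3.5.7:** base any statement on poor practice on both error types, read beside the comparison of testing policies.
5. **Burden:** say explicitly that it is estimated from central positivity on all samples.

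The cost is a wording change and one extra tabulation of data already collected. Estimates will be imprecise in small strata, so single-site rates should not be interpreted.

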### 3.2 Case control study- objective 1.3 (outcomes)

#### 3.2.1 Study rationale

Morbidity and all-cause mortality in relation to CDI within hospitals have been extensively studied . However, CDI outcomes in community settings, including nursing/convalescent homes, are poorly understood. In addition, research studies have concentrated on one area of healthcare, i.e. either a hospital or a community setting, without examining the interplay between these two settings. It is plausible that a patient with hospital acquired CDI, who recovers and is discharged into the community, may suffer a recurrence that is diagnosed empirically (i.e. without testing) or via a different laboratory from the index diagnosis. Currently, such outcomes are not captured by either surveillance or research. Given that CDI cases occur within all parts of the healthcare system, it is imperative that data relating to recurrence, morbidity and mortality from the healthcare system as a whole are studied to understand the true disease burdens and the interplay between settings.

#### 3.2.2 Outcome measures

Primary outcome measure: Crude mortality at 30 days and 6 months after the sample was taken will be compared between case and controls, those that received a correct diagnosis at the original hospital and those that were 'missed' (either due to lack of testing or inadequate testing) and between community and hospitalised patients.

Secondary outcome measures: Patient length of stay, severity of infection (e.g. WCC, serum albumin, temperature), need for escalation of medical/surgical care due to gastrointestinal disease, post-infectious sequelae.

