#### 3.2.6 Data collection

Data will be collected via a standardised CRF, with a full supporting SOP. The CRF will be completed by the clinical care team at the participating site that submitted the sample (during O1.1). The CRF will not contain any participant identifiable data; all data will be held against a pseudoanonymised study code, with the link back held by the clinical care team only. COMBACTE-CDI investigators will not access participant's notes or access the link back. Once the CRF data has been collected and validated and verified the link-back will be destroyed by the local study site.

Data will be collected on the following variables on outcomes of CDI;

- Evidence of other enteric pathogens (+/- 7 days of the original sample)?
- Symptoms at time of the sample
- Alternative cause for the patient's diarrhoea documented (e.g. laxatives, pathogen)?
- Duration of diarrhoea/non-normal bowel habit?
- Primary/recurrent CDI
- Antibiotics at the time of the sample or the preceding 3 months?
- Evidence of colitis?
- Evidence of post-infectious diarrhoea

- CDI Severity markers (Temperature (nearest reading +/- 3 days of the sample), serum creatinine (nearest reading +/- 3 days of the sample), White cell count (nearest test +/- 3 days of the sample)
- Treatment for CDI episode
- Was treatment for CDI/diarrhoea escalated medical/surgical?
- Outcome 30 days and 6 months after the sample (discharged, in-patient, died)
- Length of stay

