#### 5. Handling of missing values and other data conventions

Where data is unknown, 'data unavailable' will be entered onto the data management system. Patterns of missing data will be described. Where an individual has a missing value for one of the study outcomes, they will be excluded from the analysis of that outcome. Sensitivity analysis can be used to determine the potential effect of missing data.

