#### 7.2 Univariate analysis

Univariate analysis will be used to assess outcomes and risk factors; continuous variables will be compared between cases and controls by t-test; categorical variables will be compared between cases and controls by chi-squared (fishers exact where numbers are below 5). Risk ratios (Odds ratio if it is case control study) will be calculated for CDI cases with identified variables of interest. Univariate analysis will be used to assess consistency between countries and between different healthcare settings.

The variables to be included in the univariate analysis are shown in the table in appendix 1.

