10.3	If the sample was	Binary	Univariate/multivariate	Up to six months		
	taken as a hospital	-		after the index		
	inpatient, was the			sample		
	patient discharged	Continuous	Univariate/multivariate			
	>30 days after the	(no. of				
	sample	days)				
If the sam	ple was taken as a con	nmunity				
patient	•	-				
10.4	Was the patient	Binary	Univariate/multivariate	Up to 30 days		
	admitted to			after the index		
	hospital			sample		
10.4.1	If yes, please give	Continuous	Univariate/multivariate	Up to 30 days		
	dates of the	(no. of		after the index		
	subsequent	days)		sample		
	hospital admissions					
If the sam	If the sample was taken as a hospital inpatient or a community patient					
10.5	Did the patient die	Binary	Univariate/multivariate	Up to 30 days		
	in the 30 days after			after the index		
	the sample			sample		
		Continuous	Univariate/multivariate			
		(no. of				
		days)				
10.5.1	If yes, was the	Binary	Univariate/multivariate	Up to 30 days		
	death linked to CDI			after the index		
				sample		
10.6	Was the patient	Binary	Univariate/multivariate	Up to six months		
	admitted to			after the index		
	hospital between			sample		
	30 days and 6					
	months after the					
	sample					
10.6.1	If yes, please give	Continuous	Univariate/multivariate	Up to six months		
	the dates of	(no. of		after the index		
	hospital admissions	days)		sample		
10.7	Did the patient die	Binary	Univariate/multivariate	Up to six months		
	between 30 days			after the index		
	and 6 months after			sample		
	sample?	Continuous	Univariate/multivariate			
		(no. of				
		days)				
10.7.1	If yes, was the	Binary	Univariate/multivariate	Up to six months		
	death linked to CDI			after the index		

		sample

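### SAP Appendix 1 records later death only from 30 days to 6 months and defines no cumulative variable, so the six-month mortality in the protocol's primary outcome is not among the variables to be analysed

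*Protocol*

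**What the plan says.** Protocol 3.2.2 gives the primary outcome for objective 1.3: "Crude mortality at 30 days and 6 months after the sample was taken will be compared between case and controls". Protocol 3.2.6 lists the matching CRF item as a status at each time: "Outcome 30 days and 6 months after the sample (discharged, in-patient, died"). Both run from the sample date, so a patient who dies on day 10 is dead at 30 days and also at 6 months.

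SAP Appendix 1 asks two questions, each opening "Did the patient die". Item 10.5 covers death "in the 30 days after" the sample. Item 10.7 covers death "between 30 days" and 6 months. Each has a yes/no part and a number of days listed as continuous, and each is marked for univariate and multivariate analysis.

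SAP 7.2 ties the analysis to that table: "The variables to be included in the univariate analysis are shown in the table in appendix 1". Its test rules are a t-test for continuous variables and, for the rest, "categorical variables will be compared between cases and controls by chi-squared", with Fisher's exact test for small numbers.

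SAP 5 states: "Where an individual has a missing value for one of the study outcomes, they will be excluded from the analysis of that outcome".

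No other SAP section supplies a mortality endpoint. Section 2.5 speaks of outcomes in general, 6.1 defines only CDI as the outcome, and 7.3 models case or control status as the dependent variable.

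**The concern.** The two death items do not overlap, and the SAP never joins them. Followed as written, the 30-day half of the primary outcome is analysed correctly through 10.5. The six-month half is represented only by 10.7, which leaves out every death in the first 30 days.

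If CDI kills mainly early, those are the deaths that distinguish cases from controls. A table headed six-month mortality but built from 10.7 could then show no difference, or one in the wrong direction.

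The denominator of 10.7 is also open. A patient who died by day 30 could be entered as no, or left blank and dropped under SAP 5. The two codings give different answers, and neither is the protocol's endpoint.

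A related problem affects days to death. A continuous variable that exists only for those who died would be compared by t-test among the dead alone, separately in each window. That comparison says nothing about how many died.

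**Working it through.** **Inputs.** SAP Table 1 gives 103 + 71 + 39 = 213 cases and 512 controls, 725 in all. Neither document gives a mortality rate, an effect size or a power calculation for mortality, so there is no stated figure to reproduce. All mortality rates below are assumptions.

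**Notation.** Let a and b be the 30-day risks of death in cases and controls. Let hc and hk be the risks from 30 days to 6 months among 30-day survivors.

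- Protocol endpoint: a + (1 − a)hc v b + (1 − b)hk
- Item 10.7, early deaths coded no: (1 − a)hc v (1 − b)hk
- Item 10.7, early deaths excluded: hc v hk

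**Base illustration** (a = 15%, b = 5%, hc = hk = 10%):

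- Protocol endpoint: 0.15 + 0.85 × 0.10 = 23.5% v 0.05 + 0.95 × 0.10 = 14.5%; risk ratio 1.62
- 10.7 coded no: 0.85 × 0.10 = 8.5% v 0.95 × 0.10 = 9.5%; risk ratio 0.89
- 10.7 with early deaths excluded: 10% v 10%; risk ratio 1.00

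**When the direction reverses.** Under the first coding, 10.7 is lower in cases when hc/hk < (1 − b)/(1 − a). Equal later risk is enough whenever a > b. With later risk 10% in both groups:

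| 30-day risk, cases v controls | Cumulative | 10.7 coded no | Reversal if hc/hk is below |
|---|---|---|---|
| 10% v 5% | 19.0% v 14.5% | 9.0% v 9.5% | 1.06 |
| 15% v 5% | 23.5% v 14.5% | 8.5% v 9.5% | 1.12 |
| 20% v 5% | 28.0% v 14.5% | 8.0% v 9.5% | 1.19 |
| 30% v 10% | 37.0% v 19.0% | 7.0% v 9.0% | 1.29 |

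With equal later risks of 10% to 20% and 30-day risks of 10% to 30% v 5% to 10%, the cumulative difference runs from +4.0 to +18.0 points. The 10.7 difference runs from −0.5 to −4.0 points. If early deaths are excluded, equal later risk gives a null, and reversal needs hc < hk.

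**When it does not reverse.**

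- With 15% v 5% early and about 15% v 10% later, at the planned numbers, 10.7 coded no gives 12.7% v 9.6%, against a cumulative 27.7% v 14.6%.
- With 6% v 5% early and 20% v 10% later, the cumulative figures are 0.06 + 0.94 × 0.20 = 24.8% v 14.5%, odds ratio 1.94. Item 10.7 coded no is 0.94 × 0.20 = 18.8% v 9.5%, odds ratio 2.21. Here 10.7 overstates the odds ratio.

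Under this coding the cumulative difference minus the 10.7 difference is exactly a − b. The absolute difference is therefore always understated when a > b. The ratio measures carry no such guarantee.

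**At the planned numbers**, with counts close to the base illustration (30-day deaths 32/213 v 26/512, later deaths 18 v 49):

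- Cumulative: 50/213 (23.5%) v 75/512 (14.6%), odds ratio 1.79, p = 0.004
- 10.7 coded no: 18/213 (8.5%) v 49/512 (9.6%), odds ratio 0.87, p = 0.64
- 10.7 in 30-day survivors: 18/181 (9.9%) v 49/486 (10.1%), odds ratio 0.98, p = 0.96

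**Days to death.** With the same counts, the t-test on the 10.5 day count would use 32 + 26 = 58 of 725 patients, and that on the 10.7 day count 18 + 49 = 67.

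**The case against.** Appendix 1 reads largely as a list of CRF questions, and splitting death into two windows is a natural form layout. The protocol still defines the endpoint, nothing in the SAP says it is replaced, and the two items together rebuild it exactly. The time-window column for 10.7 runs up to six months from the index sample, which might hint at a cumulative meaning. Item 10.5 is analysed in its own right, so an early excess would be visible beside 10.7.

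Much of this stands: no data are lost, and a careful analyst would probably combine the items. It does not close the gap, because SAP 7.2 names the Appendix 1 table as the list of variables to analyse and the combined variable is not on it. The time-window entry does not settle the matter either. Items 10.3 and 10.6 carry the same label although their wording also starts after 30 days.

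A reader might infer more than the text allows: that the SAP counts patients dead by day 30 as free of the event on 10.7. It says no such thing. If those patients are left blank, SAP 5 excludes them, and the base illustration gives a null result and no reversal. Even under the other coding, the reversed difference at the planned sample size (p = 0.64) would be read as no difference, not as benefit in cases.

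**Conclusion.** The point holds as a mismatch between protocol and SAP. From the text alone, 10.7 excludes deaths in the first 30 days, no cumulative variable is defined, and the coding of early deaths on 10.7 is not stated. So 10.7 analysed as listed is not the protocol's six-month mortality, and the t-test on days to death compares only those who died.

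The size depends on assumed rates. With 15% v 5% early and 10% later in both groups, a 9.0-point cumulative excess becomes −1.0 point or zero, according to the coding. The documents do not support saying that the difference will reverse, or that 10.7 must understate every effect measure. Reversal depends on both the coding and the later risks, and the odds ratio can be overstated when later risk is much higher in cases.

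**What to change.** Add to the SAP:

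1. **Derivation.** Six-month death is yes if 10.5 is yes or 10.7 is yes. The denominator is all patients with known status at six months, and a 30-day death counts as known. Use this variable for every six-month mortality comparison in Protocol 3.2.2.
2. **Item 10.7.** State how 30-day deaths are coded. If 10.7 is shown separately, restrict it to 30-day survivors and label it so.
3. **Days to death.** Replace the t-test with a Kaplan-Meier comparison from the sample date to 6 months, built from the day counts in 10.5 and 10.7.

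Cox regression adjusted for age, sex and setting is an optional supporting analysis. It is not needed to deliver the crude mortality that the protocol specifies.

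The cost is a few lines of SAP wording and a small amount of extra analysis. The data are already on the CRF.

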#### 3.2.7 Data analysis

Comparisons will be made between recurrence/Morbidity/Mortality (crude and attributable) rates in different healthcare settings and countries. Outcomes will also be compared for different strain types (as identified in O1.2).

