#### 2.5. Analysis objectives

The main objectives of the analyses are to;

- 1. Determine the outcomes of cases (of each classification) vs controls, and compare between countries and hospital vs community cases
- 2. Determine the risk factors for cases (of each classification) vs controls, and compare between countries and hospital vs community cases

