#### 4.2 Analysis sets and subgroups

Data will be analysed to determine the outcomes and possible risk factors for CDI based on the different diagnostic criteria. Comparisons will be made between outcomes and risks for different countries and healthcare settings (hospital, community). Sample size will be too small to perform subgroup analysis within each country.

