#### 7.3 Regression analysis (or Multivariate analysis)

To evaluate risk factors considering confounding, unconditional logistic regression analysis will be perform with case/control as dependent variable, and all variables listed in the univariate analysis as independent variables.

To build the logistic regression model, we will apply a stepwise forward selection to identity risk factors. The process of the forward selection will be recorded to rank the risk factor.

The regression analysis will be performed separately for the three age groups (18-49,50-64 and 65+ years). If there is a reasonable sample size analysis will also be performed for the age group <18 years.

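### Mortality in missed versus correctly diagnosed CDI is part of the protocol's objective 1.3 primary outcome, but neither protocol 3.2.7 nor the SAP plans that comparison

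*Protocol*

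**What the plan says.** Protocol 3.2.2 states the objective 1.3 primary outcome: "Crude mortality at 30 days and 6 months after the sample was taken will be compared between case and controls". The same sentence continues to two further comparisons: "those that received a correct diagnosis at the original hospital and those that were 'missed" (through lack of testing or inadequate testing), and community versus hospitalised patients.

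The protocol's own analysis section for this objective, 3.2.7, reads: "Comparisons will be made between recurrence/Morbidity/Mortality (crude and attributable) rates in different healthcare settings and countries". It adds strain types. It does not mention missed diagnoses.

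The SAP's outcome objective (2.5) is: "Determine the outcomes of cases (of each classification) vs controls, and compare between countries and hospital vs community cases". SAP 4.2 adds: "Comparisons will be made between outcomes and risks for different countries and healthcare settings (hospital, community". On methods, SAP 7.2 says "categorical variables will be compared between cases and controls by chi-squared", and SAP 7.3 says "unconditional logistic regression analysis will be perform with case/control as dependent variable".

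The information needed to classify a patient as missed is collected elsewhere. Protocol 3.1.6 lists "CDI test result for that sample at the submitting laboratory". Protocol 3.1.7 defines a missed diagnosis as a false negative at the site or a sample not tested there, but uses it only to compare countries and sample source sites.

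**The concern.** The protocol names three contrasts in its primary outcome sentence, and the SAP carries through two. The third has no objective, definition, method or stated precision in the SAP.

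What is at stake is prespecification. Without a plan, the analyst must choose after the deaths are known which central assay defines a true case, whether untested and falsely negative patients are pooled, and which time point leads. These choices are not trivial. Protocol 3.1.2 counts missed cases against optimised testing as primary and against the novel assay as secondary. The SAP has three case classes. Each choice changes who counts as missed.

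**Working it through.** **1. The sections side by side**

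| Comparison in protocol 3.2.2 | Protocol 3.2.7 | SAP 2.5 | SAP 4.2 | SAP 7.2 | SAP 7.3 |
|---|---|---|---|---|---|
| Cases v controls | not named | yes, by class | by diagnostic criteria | yes | yes, as dependent variable |
| Community v hospital | yes | yes | yes | consistency check | no |
| Correctly diagnosed v missed | no | no | no | no | no |

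**2. Could an existing SAP analysis supply it?**

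- The case classes (SAP 2.1, 4.1.1, 6.1) are set by central CCNA, Simoa, and culture or toxin gene results. A CCNA-positive patient may have been found or missed locally, so class is not missed status.
- Missed versus diagnosed is a contrast within cases. The SAP 7.3 model has case/control status as its dependent variable, which does not vary among cases. It therefore cannot express this contrast. The SAP 7.2 tests set cases against controls.
- Protocol 3.1.7 analyses missed diagnoses, but not against mortality.

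**3. Could it be done with data in hand?** Yes. The local result arrives with the samples (protocol 3.1.6). Deaths are Appendix 1 items 10.5 (within 30 days) and 10.7 (30 days to 6 months). Data are held against the study number, so the two sources can be joined.

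**4. Numbers available.** From SAP Table 1: 103 CCNA positive + 71 Simoa only + 39 free-toxin negative = 213 cases. CCNA-negative cases are 71 + 39 = 110. The documents give no missed share, no expected mortality and no power for this contrast, so there is no stated figure to reproduce.

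**5. Illustrative precision.** Assumptions: mortality about 15% in both groups, missed share 25% or 40%. With a missed and b diagnosed cases,

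half-width = 1.96 × √[0.15 × 0.85 × (1/a + 1/b)]

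| Cases | Missed share | a, b | Half-width (points) |
|---|---|---|---|
| 103 (CCNA positive) | 25% | 25.75, 77.25 | 15.9 |
| 103 | 40% | 41.2, 61.8 | 14.1 |
| 213 (all classes) | 25% | 53.25, 159.75 | 11.1 |
| 213 | 40% | 85.2, 127.8 | 9.8 |

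First row worked: 1/25.75 + 1/77.25 = 0.0518; × 0.1275 = 0.00660; square root 0.0813; × 1.96 = 0.159.

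**6. Illustrative power** (two-sided 5%, pooled variance under the null). Over a missed share of 20-50% and mortality of 5-20% in diagnosed cases, power to detect mortality 10 points higher in missed cases is 31-69% with 213 cases and 18-42% with 103.

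**7. Deaths available to a model.** 0.15 × 103 ≈ 15 and 0.15 × 213 ≈ 32.

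**The case against.** The strongest reply is that nothing is lost: the local result is held against the study number, the protocol records and defines missed diagnoses, and the SAP lists only its main objectives. This stands in part. A reader might infer that the study could not report the comparison if the SAP were followed. The documents do not support that. The comparison could be made, but it would be unplanned.

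A reader might also take the absence of the local index-sample result from SAP Appendix 1 as proof that the variable is unavailable. It is not. SAP 2.3 presents Appendix 1 as the list for the clinical report form, and the central CCNA and Simoa results that the SAP analyses by are not in it either.

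Nor can the SAP alone be faulted, or said to supersede the protocol's list. Protocol 3.2.7 omits the contrast too, and nothing in either document says that the SAP replaces 3.2.2.

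The protocol's stated purpose for identifying missed cases is to estimate the true burden of disease. That count and its analysis in 3.1.7 are unaffected.

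Finally, one may argue that the comparison is too imprecise to be worth planning. The imprecision is real, but it is a reason to state expected precision and report intervals. It does not justify leaving out a named primary comparison without comment.

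**Conclusion.** The point holds as a gap in prespecification. Of the three comparisons in the objective 1.3 primary outcome, one, correctly diagnosed versus missed, appears in no analysis section of either document. This is a matter of text and rests on no assumption.

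The figures are illustrative. With 25-40% missed and about 15% mortality, both assumed, the half-width is about 10-16 points: 14-16 for CCNA-positive cases alone and 10-11 for all cases. Against 15% mortality that is roughly two-thirds of the rate or more. It would therefore be wrong to infer that the study can answer this question firmly. It can give an estimate with a wide interval.

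**What to change.** Add to SAP 2.5 and 7 a comparison, among cases, of crude 30-day and cumulative 6-month mortality in correctly diagnosed versus missed patients.

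- **Outcome:** 30-day death from item 10.5. For 6 months, combine items 10.5 and 10.7, because 10.7 alone leaves out the early deaths.
- **Exposure:** the local index-sample result from protocol 3.1.6, linked by study number. Define missed as in 3.1.7: not tested, or false negative locally.
- **Reference standard:** state it. Make toxin-positive cases the main analysis and show the 71 Simoa-only and 39 free-toxin-negative cases separately. In those 110 patients a negative local result may reflect assay sensitivity and not a diagnostic failure.
- **Reporting:** risk differences with 95% CIs, and a sentence in the SAP that precision is limited, giving the range above with its assumptions.
- **Adjustment:** the protocol specifies crude mortality. With about 15-32 deaths under the 15% assumption, any adjusted analysis should be supportive and use few covariates.

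Name the comparison in protocol 3.2.7 as well, so that it agrees with 3.2.2. If the comparison was dropped on purpose, document the reason and amend the primary outcome in 3.2.2.

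The cost is SAP wording, one data linkage and a small amount of extra analysis with wide intervals. No new data collection is needed.
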